Two such skills-based self-management techniques that may contribute to better pain management and improvements in psychological functioning and sleep quality in Veterans are self-hypnosis (HYP) and mindfulness meditation (MM). Both HYP and MM are easily taught and learned, and therefore could be seamlessly incorporated into clinical practice in VA hospitals and clinics across the country. However, *at this point in time, little is known about the efficacy of HYP and MM interventions for chronic pain in Veteran populations, their effects on co-morbid conditions, and their biological and psychological mechanisms.* Such information is critical to the development of strategies to efficiently and cost-effectively maximize their efficacy and to ensure optimal implementation.

The purpose of this randomized controlled trial is to test the efficacy and mechanisms of HYP and MM on chronic pain in 240 Veterans. Participants will be randomly assigned to 8 group sessions of (1) HYP, (2) MM, or (3) an education control condition (ED). Primary (characteristic pain intensity) and secondary outcomes will be assessed at pre-treatment, three times during treatment, post-treatment, and at 3- and 6-month follow-up. Potential treatment moderators and mediators will also be assessed.

The study will address two aims.

Aim 1: Determine the efficacy of 8 sessions of group delivered HYP and MM training for reducing characteristic pain intensity in Veterans, relative to 8 sessions of ED. The hypothesis associated with Aim 1 is:

Hypothesis 1: *Primary Study Hypothesis.* Veterans receiving 8 sessions of HYP or MM training will report significantly greater pre- to post-treatment decreases in average pain intensity than Veterans receiving 8 sessions of ED.

Aim 2: Evaluate the moderation effects of brain states (as measured by EEG) on response to HYP and MM, relative to ED. The hypothesis associated with Aim 2 is:

Hypothesis 2: *Brain State Moderating Hypothesis (Secondary)*. Pain reduction with HYP and MM will be significantly associated with different patterns of baseline brain activity. Specifically, participants who report the most pain reduction with HYP will evidence higher levels of global theta activity and lower levels of left frontal gamma activity at baseline. Participants who report the most pain reduction with MM will evidence lower levels of alpha activity at baseline. Baseline brain activity will not be significantly associated with pain reduction following ED.

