In addition to testing the above specific hypotheses, we will use the data obtained in this study to further explore (1) the effects of HYP and MM relative to each other and to the ED control condition on key co-morbid symptoms and conditions other than pain intensity; (2) the longer-term (up to 6 months) effects of HYP and MM, relative to ED; and (3) additional potential moderators (e.g., hypnotizability, treatment outcome expectancies, treatment motivation, demographic variables, pain type [neuropathic vs. nociceptive], cognitive functioning) and mediators (changes in EEG activity, pain acceptance, catastrophizing, mindfulness, therapeutic alliance, amount of skill practice between sessions) of treatment outcome.

Sub-Study:

A significant barrier to advancing science regarding pain and sleep is the lack of precise, objective sleep measurements.^{31,32} Chronic pain studies reporting on sleep typically rely on self-report,³¹ which limits confidence in sleep-related findings due to report and recall bias.³³⁻³⁶ The study will increase our understanding by adding wrist actigraphs – small, wrist-watch sized activity monitors worn on the wrist – to unobtrusively capture sleep/wake activity data in a trial of non-pharmacological pain interventions. Actigraphs are the technology standard for objective, naturalistic assessment of sleep.³⁷

Duration of sleep has been linked to improvements in pain reports³⁸ while sleep restriction has been found to increase pain perception and decrease ability to disengage from pain.³² Sleep deprivation reduces the pain threshold and alters levels of interleukins, suggesting an inflammatory response to sleep loss³⁹ which potentiates pain.⁴⁰ However, to what extent such potential mechanisms play a role in chronic pain, and whether or not sleep is a viable target for interventions to mitigate chronic pain, remains to be investigated.

The purpose of the sub-study is to examine how sleep relates to chronic pain within the context of the randomized controlled trial with a sample of up to 435 480 195 Veterans. Participants in the sub-study will wear an actigraph device and complete sleep/wake diaries to assess sleep quality and duration at pre-treatment, post-treatment, and at 3-month follow-up. The sub-study will address two aims.

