The assessment period described above will be completed prior to initiating treatment, and then after completion of treatment sessions #2, 4 and 6 and 8 (i.e. post-treatment), and 3 and 6 months following the end of treatment for a total of seven times. These assessment periods that occur following the start of treatment will also include questions about group climate, therapeutic alliance with the group clinician, treatment satisfaction, feedback about the treatment modality, and overall improvement since the participant began the pain program. The open-ended questions regarding treatment satisfaction and feedback on treatment modality will be collected by an unblinded staff member. Group Comfort Questions will be administered by an unblinded staff member at any time after session 8 (final group session). This assessment is optional. The window is from post-treatment until the participant is disenrolled.

Staff will send via USPS mail a reminder letter prior to the 3- and 6-month assessment periods.

As mentioned above, during the consent process research staff will provide participants with a response key to help answer questions asked during the telephone assessment periods. Participants may request research staff send another response key to them if they lose the key during study participation. Research staff will send the response key along with a cover letter via USPS mail.

Participants will be compensated \$25 for the completion of each assessment period via a check written from the Seattle Institute for Biomedical and Clinical Research (SIBCR). The check will be sent via USPS mail and accompanied by a payment cover letter.

The pre-treatment assessment period may take place up to four weeks prior to the start of the treatment groups for that particular cohort.

D6I. Randomization

Enrolled participants who complete the required baseline components (cognitive assessment, hypnotic and relaxation exercise, baseline data form, and pre-treatment assessment period) will be randomized in stratified blocks to ensure that participants with each sex/gender and pain type (neuropathic, non-neuropathic, mixed or undetermined) have an equal chance of being randomized to one of the 3 conditions. Stratification will assure that the treatment groups are balanced regarding each stratification variable, so that the estimated effect of the treatment is not biased due to differences in distribution of sex/gender or type of pain.

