The goal of mediation analyses is to examine whether group assignment (determined by randomization at baseline) impacts the change in pain intensity (primary outcome) from baseline to post-treatment through indirect effects on the hypothesized mediators (measured midway

between baseline and post-treatment). Our potential mediators have been identified a priori and are shown in the table of measures (Table 4).

To evaluate the association between intervention type, potential mediating factors, and change in pain intensity, we will first run models with individual mediators to get unadjusted estimates and to estimate the degree of confounding in subsequent multivariate models. Per Hayes & Rockwood's 2017 recommendations, we will test multiple mediators in the same model, to more accurately reflect our theoretical understanding of parallel biological and psychological mediating processes, and to facilitate comparison of the size of indirect effects through different mediators. Mediators to be included in the model include change in EEG composite scores for theta, alpha, beta, and gamma bandwidths, pain acceptance, catastrophizing, mindfulness, therapeutic alliance, and skill practice. Also per the recommendations of Hayes and Rockwood (2017), we will compute bootstrap confidence intervals for the indirect effects. All mediation analyses will be done using PROCESS, a free downloadable add-on available for SPSS and SAS (the analysis packages we will use for the study's data analysis). PROCESS includes the computational code to generate a primary estimate for the mediation model which represents the indirect, or mediated effect, and allows for inclusion of moderator variables.

Our study is longitudinal and, in addition to posttreatment assessments, we have collected data at 3- and 6-months post-treatment on outcomes and all other variables (mediators and moderators). While the approach used in the PROCESS software can be somewhat adapted for longitudinal analysis, the most appropriate analysis would be longitudinal structural equations models, particularly latent growth models (e.g., Goldsmith et al. 2018). These models require specialized software such as AMOS or LISREL and are beyond the scope of our exploratory aims. If we are able to access such statistical resources in the future, however, we would like to leverage this dataset for these exploratory purposes.

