Hypnotic and Relaxation Exercise		X															
Baseline Data and Demographic Form		X															
Pain Intensity (Primary Outcome)			X			X			X			X			X	X	X
Secondary Outcomes (e.g. Depression, Anxiety)			X			X			X			X			X	X	X
EEG Data (Mediators: Biological)			X												X		
Mediators: Psychological (e.g. Pain Acceptance, Catastrophizing)			X			X			X			X			X	X	X
Pain Intensity, Comfort Levels				X	X		X	X		X	X		X	X			
Treatment Homework Completion				X	X		X	X		X	X		X	X			
Participant Engagement				X	X		X	X		X	X		X	X			
Adverse Events				X	X	X	X	X	X	X	X	X	X	X	X		

* Onset of both enrollment and pre-treatment relative to the onset of treatment may vary given the timing of group sessions

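### The mediation model relates mid-treatment acceptance, catastrophizing and mindfulness to pain change over the whole baseline-to-post period without adjusting for pain at the mediator's own assessment, so any effect of early pain relief on these scales is counted in the indirect effect

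*Combined protocol and SAP*

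**What the plan says.** The Précis and A2 place the primary and secondary outcomes before treatment, "three times during treatment, post-treatment, and at 3- and 6-month follow-up. Potential treatment moderators and mediators will also be assessed". A2 lists as exploratory targets the "mediators (changes in EEG activity, pain acceptance, catastrophizing, mindfulness, therapeutic alliance, amount of skill practice between sessions) of treatment outcome". The Mediation analyses text in D6x sets out to examine whether assignment "impacts the change in pain intensity (primary outcome) from baseline to post-treatment through indirect effects on the hypothesized mediators (measured midway" between baseline and post-treatment. It does not say which assessment is midway.

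On model content it says: "Mediators to be included in the model include change in EEG composite scores for theta, alpha, beta, and gamma bandwidths, pain acceptance, catastrophizing, mindfulness", followed by therapeutic alliance and skill practice. The one step on confounding is this: "we will first run models with individual mediators to get unadjusted estimates and to estimate the degree of confounding in subsequent multivariate models". Bootstrap intervals come from PROCESS. Pain at the mediator's assessment, a mid-to-post outcome and a reverse-direction test are not mentioned.

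The data for all three exist. D6k schedules the assessment period before treatment, "then after completion of treatment sessions #2, 4 and 6 and 8 (i.e. post-treatment", and at 3 and 6 months. Table 5 marks average pain, acceptance, catastrophizing and mindfulness as during-treatment and post-treatment measures. Appendix 1 shows the row "Mediators: Psychological (e.g. Pain Acceptance, Catastrophizing" ticked at the 2-, 4- and 6-week assessments, as is pain intensity.

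The same D6x text calls longitudinal structural equation models the most appropriate analysis and puts them beyond scope. For the sleep sub-study (aim 2), D6x relates early sleep change to later pain change, and the reverse.

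**The concern.** The outcome window opens before the mediator is measured. Whatever part of the pain change has occurred by the midway assessment precedes the mediator and cannot be its effect at that point. If pain falls first and a person then catastrophizes less or accepts pain more, the mediator and the total pain change are correlated because both reflect early relief. The product of the two paths is then positive even if the mediator has no effect on later pain.

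Adjusting for baseline pain does not remove this, because the common cause is pain change after baseline. Comparing single- with multi-mediator models does not remove it either, because none of the listed mediators is mid-treatment pain.

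The mechanisms of self-hypnosis (HYP) and mindfulness meditation (MM) are part of the trial's stated purpose. At stake is whether a reported indirect effect can be read as a mechanism rather than a consequence of pain relief.

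**Working it through.** **1. Inputs from the plan (D6z).** Assumed pain decreases are 0.3 for education (ED), 0.8, 1 and 1.4 for HYP, and 0.6, 0.8 and 1 for MM. The SD of change is at most 1, with 80 completers per arm. Differences from ED are therefore:
- HYP: 0.8 − 0.3 = 0.5, 1 − 0.3 = 0.7, 1.4 − 0.3 = 1.1
- MM: 0.6 − 0.3 = 0.3, 0.8 − 0.3 = 0.5, 1 − 0.3 = 0.7

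**2. The plan's own figure.** There is none for mediation. The sample-size statement does reproduce. In the least favourable case (0.3/0.8/0.6, SD 1) the mean is 0.567 and the squared deviations sum to about 0.127, so λ = 80 × 0.127 ≈ 10.1. The F test with 2 and 237 df has power 81.6%, and 78 per arm would give 80%.

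**3. Why the indirect effect is not zero.** Let Δ be the arm difference, s the share of it present at mid-treatment, r the within-arm correlation of the mediator with same-period pain change, and ρ the correlation of mid with post-treatment pain change. Scale both pain changes to SD 1 and let the mediator respond only to early pain change. Then:
- arm-to-mediator path: a = r·s·Δ
- mediator-to-outcome path without mid-treatment pain: b = r·ρ
- indirect effect: a·b = s·r²·ρ·Δ, although true mediation is zero

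At s = 0.6, r = 0.3, ρ = 0.5 this is 0.6 × 0.09 × 0.5 = 0.027 of Δ. At r = 0.5, ρ = 0.7 it is 0.6 × 0.25 × 0.7 = 0.105 of Δ. With mid-treatment pain in the outcome regression, b = 0.

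**4. How often it would be declared.** Simulation: one active arm against ED, 80 per arm, SD 1, zero true mediation, s = 0.6, r 0.3-0.5, ρ 0.5-0.7. The documents give none of s, r or ρ.

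| Arm difference | Plan scenario | False mediation, planned model |
|---|---|---|
| 0.3 | MM low | about 3-9% |
| 0.5 | HYP low, MM middle | about 3-16% |
| 0.7 | HYP middle, MM high | about 4-23% |
| 1.1 | HYP high | about 10-49% |

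With mid-treatment pain added, the rate is 2% or less throughout.

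**5. Sensitivity to the set-up.** A three-arm simulation with baseline pain as covariate had pre-to-mid and mid-to-post changes independent with equal variance. Its indirect effect is s·r²·Δ. For HYP against ED:
- s = 0.5, r 0.2-0.6: false mediation 2.9-27.8%, 5.2-45.9% and 8.7-85.7% at differences 0.5, 0.7 and 1.1. The spurious part is 0.5 × 0.04 = 2% to 0.5 × 0.36 = 18% of the total effect.
- r = 0: about 0.1-0.2%, so the link with early pain is the source.
- Difference 0.7, r 0.3-0.5: 5.8-13.5% with 25% of the effect early, and 22.9-64.4% with 75% early.
- With mid-treatment pain added: 0.0-4.1%. With assumed measurement error of SD 0.3 in that pain score: 0.8% at r = 0.3 and 5.9% at r = 0.5.

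**6. Cost of the lagged model.** Now suppose mediation is genuine and acts on pain by mid-treatment. Assume treatment shifts the mediator 0.6 SD, the mediator-to-mid-pain path is 0.3-0.5, and persistence to post-treatment is 0.5-0.7. The planned model detects mediation in about 48-97% of trials and the lagged model in about 4-5%.

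**The case against.** The analysis is exploratory and belongs to neither aim. D6x says that significant exploratory findings only support further testing, commits to reporting every analysis, and concedes that a longitudinal model would be better. This limits the consequence and protects Aim 1. It does not cure the bias: the exploratory label is the stated reason for omitting a multiplicity adjustment, and full reporting does not separate cause from consequence.

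The simulations use one mediator at a time, while the plan goes on to several in parallel. They represent the plan's first modelling step, so the percentages are illustrative. The parallel model still leaves out the common cause.

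The strongest objection concerns the remedy. Mid-treatment pain is measured after randomisation and may lie on the path from mediator to outcome. Adjusting for it changes the question to later pain change only, and step 6 shows how much genuine early mediation would be lost. This stands, and it rules out using the lagged model as a gate.

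A reader might also infer that about half of the pain change has already happened when the mediator is measured, or that any treatment which lowers pain early will show mediation on any scale that tracks pain. The documents give no time course for pain. The lower ends of the simulated ranges are near or below 5% for all but the largest HYP difference.

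**Conclusion.** The concern holds for pain acceptance, catastrophizing and mindfulness. As written, their indirect effects include any reverse effect of early pain relief, and the plan reports nothing that would show how much. The direction follows from the model whenever early relief moves the mediator. The size does not follow from the documents: it depends on the share of effect reached by mid-treatment and on two correlations, all assumed here. A significant false result is possible but not certain, and the highest rates apply only to the largest HYP difference.

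The gap is one of silence: no section excludes mid-treatment pain. The point does not extend to EEG change, which is measured only before and after treatment, or to therapeutic alliance, which during treatment is collected only at the two-week assessment (Table 5 footnote). Nor should a reader infer that the primary comparison is affected: the Aim 1 ANCOVA contains no mediator.

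**What to change.** In the Mediation analyses text of D6x:

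1. State which of the assessments after sessions 2, 4 and 6 is midway.
2. For acceptance, catastrophizing and mindfulness, report beside the planned model a lagged model that adds same-period average pain and baseline pain to the mediator-to-outcome regression. With both pain terms included, the mediator coefficient is the same, up to sign, whether the outcome is baseline-to-post change, mid-to-post change or post-treatment pain.
3. Report the reverse direction, early pain change to later mediator change, as D6x already plans for sleep.
4. State that an indirect effect seen only in the unlagged model cannot separate cause from consequence. State also that the lagged model addresses only pain change after mid-treatment and is not a pass/fail criterion.

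The cost is some analysis-plan wording, added covariates in PROCESS and one further regression per mediator, all on data already collected. The drawback is that the lagged model misses mediation complete by mid-treatment, which is why both models need to be shown.
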